10.3 Data Analysis Plans

The change in T cell gene signature expression will be calculated for each group (pembrolizumab + entinostat compared to pembrolizumab alone) and compared between groups using a two group t-test. Similar analyses will be done for all gene signatures.

Appropriate descriptive statistics, including median, interquartile range, means, and 95% confidence intervals, will be calculated and reported for all lab values.

The analysis of the toxicity and safety will be based on the frequency of adverse events and their severity. Worst toxicity grades per subject will be tabulated for adverse events and laboratory measurements by using the National Cancer Institute- Common Terminology Criteria for Adverse Events (NCI-CTCAE version 5.0) and will be reported in the form of frequency tables. If 2 subjects have their surgical resection delayed beyond the 10 weeks from the time of initiation of study therapy due to protocol treatment-related adverse events, further enrollment to the study will be halted. Based on the nature and severity of

LCCC 1827 PI: [name], MPH Amendment 6 CONFIDENTIAL UNIVERSITY OF NORTH CAROLINA January 9, 2025

the toxicities observed, consideration will be made to amend the study (if risk of toxicity is felt to be mitigated by protocol amendment) vs terminating the study. If 4 or more patients are delayed due to protocol treatment-related adverse events, then the study will be terminated.

For subjects that undergo cystectomy, the proportion of patients who have a pathologic response to <pT2 will be reported along with a 95% confidence interval. Similarly, the proportion of patients who have a clinical complete response (cT0) will be reported separately for those undergoing cystectomy and trimodality therapy. Patients who progress prior to surgery (unlikely) or do not have surgery will still be included in this estimate and will be considered to have not been downstaged. The Kaplan Meier method will be used to estimate median times, along with 95% confidence intervals, for the secondary objectives of EFS and OS, as defined in Section 3.2.6 and 3.2.7.

Results gathered on these subjects will be highly valuable in providing information that can be used to inform power and sample size considerations for future investigations.

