5.3 Treatment Arm Assignment

Patients will be assigned to Arm 1 or 2. The allocation preference is to Arm 2 first, then Arm 1.

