7.3 Correlative Studies Procedures

7.3.1 Archival Tumor Tissue

Archived primary tumor in fixed paraffin-embedded blocks or slides from the diagnostic TURBT specimen of each subject must be requested at baseline for correlative studies. Additionally, we will request banked tissue on the subset of patients who have previously had tissue frozen via UNC's Tissue Procurement Facility's standing collection protocol, or through our group's biospecimen repository protocol (LCCC1212).

mRNA Sequencing and Gene Expression Profiling

RNA will be extracted from tumor samples, libraries will be prepared using the TruSeq RNA Access protocol. mRNA libraries will be sequenced, and relevant gene expression signatures will be evaluated, including relative expression of preand post-treatment STAT3 and NF- κ B signatures, IFN γ -related genes, MHC class I/II genes, and immune checkpoint genes and other immune gene signatures.

Immunohistochemistry

Histone acetylation (H3K9Ac and H3K27Ac) levels will be assessed via immunohistochemistry.

Whole Exome Sequencing

DNA will be extracted and whole-exome sequencing libraries will be generated. Exome sequence data will be processed using the established pipeline developed at UNC. Buccal swabs will be used as a source for normal DNA.

ChIP-Sequencing

For the subset of patients with frozen diagnostic TURBT and post-treatment surgical tissue available, we will perform ChIP-sequencing for H3K27Ac and other histone markers (H3K4Me3 and K3K27Me3, etc.) to assess where changes in histone post-translational modifications associate with active transcription.

T Cell Receptor Repertoire Profiling: immunoSEQ Assay
TCR repertoire amplification and sequencing will be done on tumor and
peripheral blood samples after DNA extraction. The TCRb CDR3 regions will be
amplified and sequenced using immunoSEQ. Pre- and post-treatment TCR
repertoire clonality will be compared to assess for an antigen-specific immune
response.

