10.0 STATISTICAL CONSIDERATIONS

10.1 Study Design/Study Endpoints

Our statistical design is based on a primary endpoint of the change in T cell immune gene signature with treatment. Based on studies in our lab that analyzed changes in immune gene signature expression with chemotherapy in pre-treatment TURBT and post-treatment surgery specimens, we hypothesize a change in Z-score of the T cell immune gene signature of approximately 0.5 with pembrolizumab alone with a standard deviation of 0.49, and a similar change with the addition of entinostat compared to pembrolizumab alone.

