10.2 Sample Size, Accrual and Duration of Accrual

We will accrue 10 subjects in each of the two study arms to detect a difference in change in expression using a two group t-test with 80% power and a one-sided alpha of 10% (will accrue N=20 total, 10 subjects in each arm). The hypothesized mean change is 0.5 in the pembrolizumab alone arm and 1.0 in the entinostat +pembrolizumab arm, and we assume a 0.49 common standard deviation.

After 5 subjects that undergo subsequent trimodality therapy are accrued to the study, the number of post-treatment surgery samples that were collected will be reviewed by the study team to ensure that adequate tumor sampling has occurred in this subset of subjectss. It will then be decided to continue the study allowing the inclusion of trimodality subjects (if post-treatment surgical sample collection was adequate) or restrict further accrual to cystectomy subjects only.

Accrual will take place over two years.

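### The primary t-test on change scores fixes the slope on baseline at 1; prespecifying adjustment for the baseline T cell signature is a cheap improvement whose gain depends on figures the plan does not give

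*Combined protocol and SAP*

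**What the plan says.** Section 10.1 states the endpoint: "Our statistical design is based on a primary endpoint of the change in T cell immune gene signature with treatment". Section 10.3 gives the whole primary comparison: the change is calculated for each arm and "compared between groups using a two group t-test", and similar analyses are planned for all gene signatures. No section names a baseline covariate for this endpoint.

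Section 10.2 sizes the trial on the same test, "using a two group t-test with 80% power and a one-sided alpha of 10" percent. Its inputs are: "The hypothesized mean change is 0.5 in the pembrolizumab alone arm and 1.0 in the entinostat +pembrolizumab arm"; "we assume a 0.49 common standard deviation"; and "will accrue N=20 total, 10 subjects in each arm".

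Two other sections bear on the point. Under section 7.3.1, "blocks or slides from the diagnostic TURBT specimen of each subject must be requested at baseline", so the baseline signature is part of the data plan for everyone. Under section 5.3, patients are assigned to an arm and "The allocation preference is to Arm 2 first, then Arm 1"; no random element is described.

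**The concern.** A change score uses baseline in one fixed way: it subtracts it, which sets the slope of post-treatment on baseline signature at 1. If the true slope is lower, subjects who start low tend to show a larger change than subjects who start high, whatever the treatment does. The two-group t-test leaves that predictable part in the error term. A difference in baseline means between the arms then also moves the contrast through regression to the mean.

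With 10 subjects per arm and a margin of about 3 points over the 80% target, precision available at no extra assay cost is worth having. Every subject who contributes a change score already has the baseline value, so the covariate is never the limiting item.

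**Working it through.** **1. The plan's own figure.** Inputs from section 10.2: difference 1.0 − 0.5 = 0.5, SD of change 0.49, 10 per arm, one-sided alpha 0.10.

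- SE = 0.49 × √(1/10 + 1/10) = 0.219.
- Noncentrality = 0.5 / 0.219 = 2.28 on 18 df.
- The noncentral t gives power 82.8% at 10 per arm and 79.6% at 9. Ten per arm is the smallest size that reaches 80%, so the plan's figure reproduces.

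**2. Adjusted analysis, equal pre and post variances.** The pre-post correlation ρ is an assumption, because the documents do not give it. Holding the change SD at 0.49, the per-time SD is 0.49 / √(2(1 − ρ)). The residual SD after regression on baseline is 0.49 × √((1 + ρ)/2), with 17 df. Estimating the slope inflates the contrast variance by 1 + 1/16 = 1.0625 on average when the arms' true baseline means are equal. The variance ratio to the t-test is therefore 1.0625 × (1 + ρ)/2.

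| ρ | Variance ratio to t-test | Mean SE | Power |
|---|---|---|---|
| t-test on change | 1.00 | 0.219 | 82.8% |
| 0 | 0.53 | 0.159 | 96% |
| 0.3 | 0.69 | 0.182 | 92% |
| 0.5 | 0.80 | 0.195 | 89% |
| 0.7 | 0.90 | 0.208 | 86% |
| 0.8 | 0.96 | 0.214 | 84% |
| 0.9 | 1.01 | 0.220 | 82.5% |
| 0.95 | 1.03 | 0.223 | 82% |

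Break-even: 1.0625 × (1 + ρ)/2 = 1 gives ρ = 0.88.

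**3. Unequal variances.** Let k = post SD / pre SD. The slope is ρk, and the variance ratio before the 1.0625 factor is (1 − ρ²)k² / (k² + 1 − 2ρk).

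- k = 1.5, ρ = 0.5: slope 0.75, ratio 0.964 × 1.0625 = 1.02, power about 82%.
- k = 2, ρ = 0.5: slope 1, ratio 1.000 × 1.0625 = 1.06, power about 81%.
- k = 1.5, ρ = 0.67: slope about 1, ratio 1.06, power about 81%.

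The worst case with comparable baselines is thus a loss of just under 2 points (82.8% to 81.1%).

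**4. Shift from a baseline difference.** Take ρ = 0.5 and equal variances, so the baseline SD is 0.49. One standard error of the difference in baseline means is 0.49 × √0.2 = 0.219, or 0.22. The change-score contrast moves by (1 − 0.5) × 0.219 = 0.11, which is 22% of the planned 0.5.

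**5. True baseline difference between arms.** The adjusted estimate equals the change-score estimate plus (1 − slope) × (Arm 2 minus Arm 1 baseline mean). Suppose Arm 2 truly starts 1 baseline SD higher and each arm regresses to its own mean. At ρ = 0.5 the change score still averages 0.50, while the adjusted estimate averages 0.50 + 0.5 × 0.49 = 0.75. At ρ = 0.7 the baseline SD is 0.633 and the adjusted estimate averages 0.50 + 0.3 × 0.633 = 0.69. If both arms instead regress to a common mean, the change score is the biased one. A 1 SD difference also costs precision: the variance ratio becomes 0.89, 1.03 and 1.17 at ρ = 0.3, 0.5 and 0.7.

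**6. Fewer evaluable pairs.** Twenty is an accrual target; section 10.2 states no allowance for unusable tissue and plans a review of sampling in trimodality subjects. With 8 pairs per arm the t-test has 75.7% power. Adjustment gives 81.9% at ρ = 0.5 and 85.9% at ρ = 0.3, under the assumptions of step 2.

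**The case against.** The strongest reply is that the planned test is valid, matches the stated endpoint and is the test used for sizing, in a study described as a proof of concept. That stands, and it limits the point to an improvement. Four stronger readings are tempting, and the documents do not support them.

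- *The analysis ignores baseline.* It does not; it subtracts it. What is missing is an estimated slope.
- *Adjustment always gives a tighter contrast.* A change score is negatively correlated with its baseline only when ρ is below pre SD / post SD. Both treatments are expected to move this signature, so a wider post-treatment spread is possible, and neither SD is given. Steps 2 and 3 show cases with no gain or a small loss.
- *The trial is underpowered or mis-sized.* Step 1 shows that it is not, on its own inputs.
- *Adjustment repairs the lack of randomisation.* Step 5 shows that when the arms' true baselines differ, the two analyses can target different quantities, and the documents cannot settle which is right. Adjusting for one noisy baseline measurement does not remove other confounding either.

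In favour of adjusting, the trade is uneven when baselines are comparable: a gain of about 9 points at ρ = 0.3 or 6 at ρ = 0.5, against a loss of at most about 2. The two specimens come from different procedures up to about 10 weeks apart with treatment between them, so a correlation near 0.9 cannot be taken for granted.

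**Conclusion.** The point holds as a modest, conditional improvement. Section 10.3 uses an unadjusted t-test on change that is valid and has 82.8% power. With equal variances, comparable baselines and a change SD of 0.49, estimating the baseline slope raises power to about 92%, 89% or 86% at correlations 0.3, 0.5 or 0.7. The gain is nil near 0.88. Where the slope of post on pre is close to 1, the adjusted analysis loses up to about 2 points. The correlation and the variance ratio are assumptions throughout, and a true baseline difference of 1 SD between arms removes the precision gain at correlations of 0.5 or more.

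**What to change.** In section 10.3, prespecify as primary a linear model of post-treatment T cell signature (or change; the arm coefficient is the same) on arm and baseline signature. Test the arm coefficient at the planned one-sided 10% and report its confidence interval. Keep the two-group t-test on change as a prespecified supportive analysis, and use the same model for the other signatures. The choice should be fixed before arm-level results are seen, since choosing between the two afterwards would invite selection.

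Because arms are assigned by preference (section 5.3), also report baseline means by arm and both estimates side by side. State that the two can disagree if true baselines differ, and that neither removes other confounding.

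The cost is a few sentences in 10.3, one degree of freedom (17 instead of 18) and a possible small loss of power. No extra subject, specimen or assay is needed.

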3.2 Secondary Endpoints

- **3.2.1** Pre- and post-treatment TCR repertoire and neoantigen changes will be defined by changes in TCR clonality and neoantigen load.
- 3.2.2 Pre- and post-treatment changes in STAT and NF-κB expression will be evaluated using mRNAseq analysis and changes in histone acetylation (H3K9Ac and H3K27Ac) levels in a subset of subjects with pre- and post-treatment tumor tissue available (diagnostic TURBT and maximal TURBT or cystectomy tissue available)
- 3.2.3 Toxicity will be evaluated according to guidelines from National Cancer Institute

 Common Terminology for Adverse Events (NCI-CTCAE) criteria version 5.0
 and include all adverse events continuing or occurring 30 days after completion of treatment
- **3.2.4** A pathologic response will be defined as <pT2 (pT0-T1N0M0) and pathologic complete response will be defined as pT0N0M0 at the time of cystectomy at the completion of study treatment.
- 3.2.5 The clinical complete response rate (cT0) is defined as cT0 at the time of maximal TURBT
- **3.2.6** EFS is defined as day 1 of neoadjuvant/protocol treatment to date of first documentation of disease progression (or until recurrence after surgery or radiation) or death due to any cause. Recurrence includes the development of second primary muscle-invasive urothelial malignancies.
- **3.2.7** Overall survival is defined as day 1 of neoadjuvant/protocol treatment to date of death due to any cause. Patients will be censored at date of last follow-up.

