4.1 Inclusion Criteria

- **4.1.1** Written informed consent obtained to participate in the study and HIPAA authorization for release of personal health information.
- 4.1.2 Subjects must agree to donate tumor tissue from their diagnostic transurethral resection of the bladder tumor (TURBT) and from their post-treatment surgery (cystectomy or repeat maximal TURBT). Subjects must also agree to donate whole blood prior to initiating therapy, during study therapy and at post-treatment surgery.
- **4.1.3** Age \geq 18 years at the time of consent.
- **4.1.4** Eastern Cooperative Oncology Group performance status of ≤ 2 .
- **4.1.5** Histological confirmation of urothelial carcinoma of the bladder; those with mixed histology, including a component of urothelial carcinoma, are eligible. Pure small cell carcinoma, pure adenocarcinoma, and pure squamous cell carcinoma are excluded.
- **4.1.6** Subject has clinical stage T2-T4a N0/X M0 urothelial carcinoma. Clinical T stage is based on the pre-study standard of care transurethral resection of the bladder tumor (TURBT) sample and imaging studies (abdominal/pelvic CT or MRI scan and CT scan of the chest performed within 4 weeks prior to treatment initiation).
- **4.1.7** Available formalin-fixed paraffin-embedded (FFPE) archival tumor specimen that contains sufficient tissue to generate at least 15 (preferably 20) unstained slides, each with tissue sections that are 5 10 microns thick.
- **4.1.8** Subject is planned to undergo definitive therapy for MIBC with either surgery (radical cystectomy) or trimodality therapy (including repeat TURBT followed by concurrent chemoradiation). Subjects undergoing trimodality therapy must be deemed to not be a candidate for radical cystectomy, or refuse radical cystectomy. Suggested chemotherapy regimens are outlined in Appendix E but not mandated by protocol.
- **4.1.9** Subject demonstrates adequate organ function as defined in the table below; all screening laboratory assessments should be performed within 10 days of treatment initiation.

System	Laboratory Value
--------	------------------

Hematological	
Absolute neutrophil count (ANC)	$\geq 1.5 \times 10^{9}/L$
Platelets	≥100 × 10 ⁹ /L
Hemoglobin	≥9 g/dL
Renal	
Estimated GFR per CKD-EPI equation	≥30 mL/min
Hepatic	
Serum total bilirubin	≤ 1.5 mg/dL (subjects with Gilbert's syndrome may be enrolled despite a total bilirubin level >1.5 mg/dL if their conjugated bilirubin is <1.5 × ULN)

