AST (SGOT) and ALT (SGPT)	\leq 2.5 \times ULN
Coagulation	
International normalized ratio (INR) OR prothrombin time (PT)	≤1.5 × ULN unless participant is receiving anticoagulant therapy as long as PT or aPTT is within therapeutic range of intended use of anticoagulants

- **4.1.10** If subject is planned to undergo radical cystectomy, subject refuses to receive or is ineligible to receive cisplatin-based neoadjuvant chemotherapy. Determination of ineligibility for cisplatin is based on at least one of the following criteria:
 - Eastern Cooperative Oncology Group performance status of 2
 - GFR per CKD-EPI equation ≤ 60 mL/min
 - NCI CTCAE version 5.0 Grade ≥ 2 hearing loss
 - NCI CTCAE version 5.0 Grade ≥ 2 neuropathy
- **4.1.11** Female subjects of childbearing potential should have a negative serum pregnancy within 72 hours prior to receiving the first dose of the study treatment. Non-childbearing potential is defined as (by other than medical reasons):
 - \geq 45 years of age and has not had menses for \geq 2 years
 - amenorrheic for <2 years without a hysterectomy and oophorectomy and a follicle-stimulating hormone value in the postmenopausal range upon pre-study (screening) evaluation
 - post hysterectomy, oophorectomy or tubal ligation.
- **4.1.12** Female subjects of childbearing potential must be willing to use an adequate method of contraception as outlined in Appendix D, for the course of the study through 120 days after the last dose of study medication.

Note: Abstinence is acceptable if this is the usual lifestyle and preferred contraception for the subject.

4.1.13 Male subjects of childbearing potential must agree to use an adequate method of contraception as outlined in Appendix D, starting with the first dose of study therapy through 120 days after the last dose of study therapy.

Note: Abstinence is acceptable if this is the usual lifestyle and preferred contraception for the subject.

- **4.1.14** Subject is able to tolerate and retain oral medication.
- **4.1.15** Life expectancy greater than 3 months.

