All Other irAEs	Persistent Grade 2 Grade 3	Withhold or discontinue based on the event e	Based on severity of AE administer corticosteroids	Ensure adequate evaluation to confirm etiology or exclude other
	Recurrent Grade 3 or Grade 4	Permanently discontinue		causes

AE(s)=adverse event(s); ALT= alanine aminotransferase; AST=aspartate aminotransferase; CTCAE=Common Terminology Criteria for Adverse Events; DRESS=Drug Rash with Eosinophilia and Systemic Symptom; GI=gastrointestinal; IO=immuno-oncology; ir=immune related; IV=intravenous; SJS=Stevens-Johnson Syndrome; T1DM=type 1 diabetes mellitus; TEN=Toxic Epidermal Necrolysis; ULN=upper limit of normal.

Note: Non-irAE will be managed as appropriate, following clinical practice recommendations.

- a AST/ALT: >3.0 to 5.0 x ULN if baseline normal; >3.0 to 5.0 x baseline, if baseline abnormal; bilirubin:>1.5 to 3.0 x ULN if baseline normal; >1.5 to 3.0 x baseline if baseline abnormal
- b AST/ALT: >5.0 to 20.0 x ULN, if baseline normal; >5.0 to 20.0 x baseline, if baseline abnormal; bilirubin:>3.0 to 10.0 x ULN if baseline normal; >3.0 to 10.0 x baseline if baseline abnormal
- c AST/ALT: >20.0 x ULN, if baseline normal; >20.0 x baseline, if baseline abnormal; bilirubin: >10.0 x ULN if baseline normal; >10.0 x baseline if baseline abnormal
- d The decision to withhold or permanently discontinue pembrolizumab is at the discretion of the investigator or treating physician. If control achieved or ≤ Grade 2, pembrolizumab may be resumed.
- e Events that require discontinuation include, but are not limited to: encephalitis and other clinically important irAEs.

Management of toxicities that are at least possibly related to entinostat, with toxicities graded by the Investigator according to the NCI CTCAE version 5.0 should be managed as follows:

Toxicity	Dose Modifications for Entinostat						
	Non-hematologic Toxicity						
Grade ≥ 3	Administer symptomatic remedies/start prophylaxis. Hold dose until recovery to Grade 1 or baseline under the following directions: If not recovered to Grade ≤ 2 within 1 week, permanently discontinue study drug.						
Grade ≤ 2	Administer symptomatic remedies/start prophylaxis.						
	Hematologic Toxicity						

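### The laboratory toxicity table takes each subject's worst grade without reference to the pre-dose grade, so a stable graded abnormality present at entry would be listed as toxicity

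*Combined protocol and SAP*

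**What the plan says.** Section 10.3 bases the safety analysis on CTCAE v5.0 grades shown in frequency tables: "Worst toxicity grades per subject will be tabulated for adverse events and laboratory measurements". Laboratory measurements are thus tabulated alongside adverse events, under the same worst-grade rule. The only other laboratory summary is a set of descriptive statistics that "will be calculated and reported for all lab values". It mentions neither change from baseline nor a layout by visit.

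Section 4.1 sets entry limits that leave room for abnormal values: hemoglobin of at least 9 g/dL and estimated GFR of at least 30 mL/min. The INR/PT limit applies "unless participant is receiving anticoagulant therapy". For cystectomy subjects, "GFR per CKD-EPI equation ≤ 60 mL/min" is one of four ways to be cisplatin-ineligible.

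Baseline is used elsewhere. The notes to the immune-related toxicity table in Section 5.4 define AST/ALT bands as ">3.0 to 5.0 x ULN if baseline normal; >3.0 to 5.0 x baseline, if baseline abnormal", with a parallel rule for bilirubin. The entinostat hold rules in the same section accept recovery to Grade 1 or to the subject's baseline. Appendix F (13.6.1) does not count fluctuation of a pre-existing condition as an adverse event unless it worsens.

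**The concern.** A worst-grade table is meant to show what happened on treatment. Where eligibility admits abnormal values and the rule ignores the entry grade, a subject whose value never moves is listed at the grade carried in. Nothing in Section 10.3 even excludes the screening and Day 1 values from the worst.

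This bears on secondary objective 2.2.3, which documents safety with and without entinostat. Under Section 5.3 arms are filled by preference, Arm 2 before Arm 1. Arm 2 also has additional exclusions in Section 4.2 (4.2.5, 4.2.16, 4.2.17 and 4.2.22). The arms may therefore differ at entry for reasons unrelated to the drugs. Anemia is a relevant case: Section 6.2.6 reports it in 47% of entinostat-treated patients on continuous dosing, and low hemoglobin is also something eligibility permits. A table that cannot separate entry anemia from new anemia blurs a signal that the trial would want to see.

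**Working it through.** **The passages side by side**

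| Item | Uses baseline? | Where |
|---|---|---|
| Laboratory worst-grade table | No | 10.3 |
| Descriptive statistics of laboratory values | No change from baseline named | 10.3 |
| AST/ALT and bilirubin bands | Yes, if baseline is abnormal | 5.4, notes a-c |
| Entinostat holds | Yes, recovery to Grade 1 or baseline | 5.4 |
| Adverse events | Yes, unworsened pre-existing conditions excluded | 13.6.1 |
| Halting and termination rule | Not applicable; uses surgery delay due to treatment-related events | 10.3 |

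**Liver tests drop out.** A subject admitted at 2.5 x ULN who stays there has a ratio to baseline of 2.5/2.5 = 1.0, below the 3.0 at which the first AST/ALT band starts. A stable bilirubin in Gilbert's syndrome also has ratio 1.0, below 1.5. The column heading of that table and Section 10.3 both cite CTCAE v5.0.

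**Hemoglobin, renal function and INR remain.** The documents give no baseline-relative rule for them, and no CTCAE cut-offs either. They therefore do not show which admitted values carry a grade.

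**Denominator.** Section 10.2 gives 10 per arm (difference 1.0 - 0.5 = 0.5, SD 0.49, one-sided alpha 10%, 80% power). By the noncentral t distribution, 9 per arm gives 79.6% power and 10 gives 82.8%, so the stated figure reproduces. It serves here only as the table denominator.

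**Illustration on assumed rates.** Let q be the share of an arm entering with a graded abnormality that does not worsen, and t the rate of new abnormality, taken as independent. Without a baseline reference, the expected share listed is q + (1 - q)t. Counting only worsening, it is t.

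| q (assumed) | Listed per 10, t = 0 | Worsened per 10, t = 0 | Listed per 10, t = 20% | Worsened per 10, t = 20% |
|---|---|---|---|---|
| 10% | 1 | 0 | 2.8 | 2.0 |
| 30% | 3 | 0 | 4.4 | 2.0 |
| 50% | 5 | 0 | 6.0 | 2.0 |

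For example, with q = 30% and t = 20%: 0.30 + 0.70 x 0.20 = 0.44, or 4.4 of 10.

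**Chance imbalance.** Suppose both arms draw from the same q, as independent binomials with n = 10, and there is no drug effect. For q = 10%, 30% and 50%:

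- A difference of at least 2 listed subjects has probability 24%, 46% and 50%.
- A difference of at least 3 (30 percentage points) has probability 6%, 22% and 26%.

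These figures assume equal prevalence in the two arms. Assignment by preference gives no such assurance.

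**The case against.** The strongest reply is that this is a table-format matter in a 20-subject translational study. Sections 5.4 and 8.4 speak of assessing subjects for toxicity that develops, which suggests new findings. Appendix F makes a laboratory result an adverse event only if it is clinically significant. Section 9.3 starts non-serious event recording on Day 1, and Section 7.1.5 records relation to study drug. No between-arm toxicity test is planned, and no decision depends on the laboratory table.

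Most of this stands, and it limits the point to one descriptive table. It does not remove it. The adverse event definition does not govern laboratory measurements that Section 10.3 tabulates in addition to adverse events, and the general wording about developing toxicity does not say what the table counts.

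Three stronger readings are tempting, and the documents do not support them:

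- A reader might infer that the safety table and the management table use different scales, with raised transaminases as the example. Both cite CTCAE v5.0, and the Section 5.4 notes already grade liver tests against an abnormal baseline.
- A reader might infer that every subject admitted on the renal criterion will be listed, and put a count on it. The share is not given. The criterion applies only to cystectomy subjects, is one of four, and is not needed by those who refuse cisplatin. Trimodality subjects are also enrolled. The scheduled chemistry panel lists creatinine and not GFR, and no cut-off is given for either.
- A reader might infer that reported adverse event rates or the stopping rule are distorted. They are protected by 13.6.1 and by the surgery-delay definition.

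**Conclusion.** The point holds for the laboratory worst-grade table, for tests without baseline-relative grading in the documents. As written, Section 10.3 mixes stable entry abnormalities with new toxicity wherever an admitted value carries a grade, and the non-randomized arms make differences in that table hard to read. The entinostat hold rules show that the protocol itself expects some subjects to enter with a graded abnormality.

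The size cannot be derived from the documents. The range of 1 to 5 subjects per arm of 10 rests wholly on assumed shares of 10% to 50% and on no drug effect. The consequence is limited to the interpretation of a descriptive secondary summary. The change is worth making because it is a better rule at almost no cost, not because any trial decision is at risk.

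**What to change.** In Section 10.3, separate the laboratory rule from the adverse event rule. Suggested text: for each laboratory test, the worst CTCAE v5.0 grade after the first dose will be cross-tabulated by arm against the last grade before the first dose (screening, or Day 1 if drawn pre-dose); only grades that exceed the pre-dose grade will be counted as laboratory toxicity.

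The Time and Events Table (Section 8.1) already schedules hematology and chemistries at screening, Day 1 and later visits, and PT/INR at screening and pre-surgery. Its footnote 2 allows recent screening results to stand for Day 1. The cost is a short amendment to the analysis text and some programming. No new data, visits or subjects are needed.
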